11.3.5 Outcome

Outcome describes the status of the AE. The Investigator will provide information regarding the subject outcome of each AE.

11.3.6 Action Taken Regarding the Investigational Drug Product

The Investigator will provide information regarding the action taken with respect to the study treatment in response to the AE.

11.3.7 Expectedness of an Adverse Event

The expectedness of all AEs will be determined according to the most recent versions of the Investigator's Brochures for casimersen and the prescribing information for eteplirsen and golodirsen.

11.3.8 Suspected Unexpected Serious Adverse Reactions (SUSARs)

Suspected unexpected serious adverse reactions (SUSARs) will be handled by appropriate Study Sponsor or designee personnel and reported within the required timelines in an unblinded fashion to regulatory authorities and IRB per the requirements of the concerned competent authorities.

11.3.9 Adverse Event Reporting

Only Treatment Emergent Adverse Events (TEAEs) will be summarized in reports. Non-emergent events will be recorded in data listings. For all AE tables, the number and percent of subjects reporting AEs (grouped by the Medical Dictionary for Regulatory Activities [MedDRA] System Organ Class [SOC] and Preferred Term [PT]) will be summarized by treatment group. In general, tables will have events categorized into all TEAEs and treatment-related TEAEs. Treatment-related TEAEs will be defined as those that the Investigator considers possibly/probably or definitely related to the study treatment.

Multiple occurrences of the same AE (at the PT level) in the same subject will be counted only once in frequency tables. If a subject experiences multiple episodes of the same event with different relationship/severity, the event with the strongest relationship and maximum severity to study treatment will be used to summarize AEs by relationship and severity.

The following summary tables will be produced:

- TEAEs
- TEAEs by severity
- Treatment-related TEAEs
- Treatment-related TEAEs by severity
- SAEs
- Deaths

In addition, all SAEs regardless of their treatment-emergent status will be summarized by SOC and PT.

The following listings will be produced:

- Non-treatment emergent AEs
- All TEAEs
- AEs leading to discontinuation
- SAE

11.4 Recording Adverse Events

All AEs/SAEs experienced from the time of informed consent/assent to the last follow-up visit will be recorded within each subject's CRF. For patients who prematurely discontinue from the study (Section 7.6), AEs will continue to be recorded until 28 days after the last study treatment infusion.

Information should include: a concise description of the event; date of event onset and resolution; determination of seriousness, severity, corrective treatment, outcome, and relationship to IP or study procedure or underlying disease; and any action taken will be recorded. Resolution occurs when the subject has returned to his Baseline state of health or further improvement or worsening of the event is not expected.

Whenever possible, a diagnosis will be recorded as an AE, rather than symptoms or isolated laboratory abnormalities related to that diagnosis. Several symptoms or laboratory results that are related to the same diagnosis can thus be part of the same AE.

A medical or surgical procedure is not an AE; rather the condition leading to the procedure should be recorded as the AE. Similarly, death is not an AE, but is rather the outcome of the AE(s) that resulted in death. If the AE(s) leading to death are not known, then death must be reported as an AE. All AEs will be followed until the resolution of AE, completion of the subject's study participation, or study termination, whichever occurs first. SAEs will be followed until resolution or until the condition stabilizes or returns to Baseline status.

11.5 Safety Reporting

The investigator or his designee will report all serious adverse events according to the following:

DSMB: The Investigator or his/her designee will report SAEs to the DSMB within the below timeframe:

- Any serious adverse event that is **fatal or life-threatening** and possibly, probably, or definitely related to one of the investigational products, regardless of expectedness, will be reported to the DSMB within **5 business days** of initial receipt of the information.
- Any serious adverse event that is unexpected and possibly, probably, or definitely related with the use of one of the investigational products (SUSAR), but is **not fatal or life-threatening**, will be reported within **5 business days** of initial receipt of the information.

FDA: The Investigator or his/her designee will report SAEs to their FDA Investigator-Initiated IND within the below timeframe:

- Any serious adverse event that is **fatal or life-threatening** and unexpected and possibly, probably, or definitely associated with the use of one of the investigational products (SUSAR) will be reported as soon as possible, but in no case later than **7 calendar days** after initial receipt of the information.
- Any serious adverse event that is unexpected and possibly, probably, or definitely associated with the use of one of the investigational products (SUSAR), but is **not fatal or life-threatening**, will be reported as soon as possible, but in no case later than **15 calendar days** after initial receipt of the information.
- If, after further evaluation, an unexpected serious adverse event that is initially considered not to be associated with the use of one of the investigational products is subsequently determined to be associated, then the event will be reported as soon as possible, but in no case later than **15 calendar days** after the determination is made.

IRB: The Investigator or his/her designee will report SAEs to the IRB within the below timeframe:

- Any serious adverse event that is unexpected and possibly, probably, or definitely related will be reported to the IRB within **5 business days** of initial receipt of the information.

Sarepta: The Investigator or his/her designee will report SAEs to Sarepta within the below timeframe:

- Any serious adverse event that is unexpected and possibly, probably, or definitely related (SUSAR) will be reported to Sarepta within **24 hours** of initial receipt of the information. All follow-up information on SUSARs will be reported to Sarepta within **24 hours** of initial receipt of the information.
- All other serious adverse events and Special Situation listings will be reported to Sarepta **monthly**, regardless of expectedness, relatedness, or if they meet the definition for unanticipated problems to the clinical trial.

Sarepta will be responsible for submitting expedited reports to their respective FDA INDs and NDAs, as applicable, all ex-US regulatory authorities, and to Investigators in ongoing studies of casimersen, eteplirsen or golodirsen.

Changes in the FDA reporting schedule will be permitted only where, under the **FDA IND** regulations [21 CFR 312(c) (3)], changes in this reporting schedule have been approved by the FDA and are reflected in the protocol. Nationwide Children's Hospital will be responsible for reporting to their Investigator-Initiated FDA IND for the product.

Relevant follow-up information will be submitted concurrently to the **FDA, IRB, DSMB, and Sarepta**, as applicable, as soon as the information is available and will be identified as such, i.e., "Follow-up IND Safety Report."

If a serious adverse event occurs after the end of a clinical trial, the event will be reported to the **FDA, IRB, DSMB** and Sarepta according to the criteria and timelines defined above for reporting SAEs during the trial.

Should a serious adverse event deemed possibly, probably or definitely related to one of the investigational products occur during administration, the product will be discontinued, appropriate treatment will be given under medical supervision and the subject will be examined as frequently as necessary thereafter until symptoms cease or stabilize.

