8.2 Treatments Administered

Eligible subjects will receive a weekly IV infusion of study treatment (30 mg/kg of casimersen, eteplirsen, or golodirsen, according to genotype) for up to 48 weeks. Subjects will be transitioned to the Sarepta Clinical Transition Program/SareptAssist after the study period for continuous weekly drug access while study sample analysis is pending.

The dose of casimersen, eteplirsen, or golodirsen will be calculated based on the most recent subject weight obtained at the site prior to the current visit. Infusion solutions of casimersen, eteplirsen, or

golodirsen are to be prepared by following the steps detailed in the study-specific Clinical Study Manual of Operations.

- Study treatment will be administered as an IV infusion over a period of approximately 35 to 60 minutes. Patients are to be closely monitored for at least 1 hour following the completion of all infusions. It is recommended that a topical anesthetic cream (e.g. lidocaine 2.5%, prilocaine 2.5%, LMX4 cream, or other per the Investigator's discretion) be applied to the infusion site prior to each administration of study treatment. Additional administration and IP details are available in the study-specific Clinical Study Manual of Operations.

An implanted venous access port may be inserted for study treatment administration at the discretion of the Investigator. After study treatment administration and the saline flush, the port may be flushed with heparin to heparin the port prior to removal of the infusion line. If study treatment is administered into an existing IV line, the line must be flushed with normal saline before and after administration of study treatment.

Subjects will have vital signs measured on infusion days within approximately 30 minutes prior to infusion and approximately 5, 30, and 60 minutes after the end of the infusion. At each infusion, concomitant medications and adverse events will be reviewed.

No other medications may be administered concomitantly during the study treatment infusion. All subjects will be observed for at least 1 hour following the end of each infusion.

The following guidelines for the timing of dosing are to be followed throughout the study:

1. Subjects should receive study treatment once every 7 days starting at the Week 1 Visit.
2. After the first infusion, a window of ± 2 days around the scheduled weekly dosing date (referenced back to the first dose at Week 1) is acceptable.

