11.5.2 Special Situations

All occurrences of pregnancy, overdose, medication error, and accidental or occupational exposure with study treatment (regardless of whether an AE or SAE has occurred) must be reported to the DSMB within 24 hours of notification and to Sarepta on monthly line listings.

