11.5.2.2 Overdose

An overdose is defined as administration of a dose that is >10% higher than the assigned dose per the protocol. An overdose will be reported even if it does not result in an AE. An overdose will be recorded on the appropriate form and sent to the DSMB or designee within 24 hours.

Medication Error

Medication Error is any preventable incident that may cause or lead to inappropriate study treatment use or patient harm, while the study drug is in the control of the healthcare professional, or in certain cases, the patient. Such incident may be due to health-care professional practice, product labeling, packaging and preparation, procedures for administration, and systems, including the following: prescribing, order communication, dispensing, nomenclature, compounding, distribution, administration, education, monitoring, and use.

Accidental/Occupational Exposure

Accidental/Occupational Exposure is the unintentional exposure to a study treatment as a result of one's professional or non-professional occupation, or accidental exposure to a nonprofessional to whom exposure was not intended (eg, study drug given to wrong patient).

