13.3 Data and Safety Monitoring Plan

13.3.1 The Data Safety Monitoring Plan

A Data and Safety Monitoring Board (DSMB) will act in an advisory capacity to review participant safety and study progress for the "48-Week, Open Label, Study to Evaluate the Efficacy and Safety of Casimersen, Eteplirsen and Golodirsen in Subjects with Duchenne Muscular Dystrophy carrying eligible DMD duplications " study.

The activities and composition of this committee will be detailed in the DSMB Charter, which will be ratified during the initial DSMB meeting, which will occur prior to the commencement of dosing of the patients.

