15.1.2 Institutional and Ethics Review

This study will be conducted in full compliance with the IRB regulations in 21 CFR 56 and/or the European Clinical Trial Directive 2001/20/EC. Before enrollment of subjects into the study, the protocol and informed assent (for subjects, if applicable) and informed consent (for parents/legal guardians) documents will be reviewed and approved by the appropriate IRB and regulatory authority. Amendments to the protocol will be subjected to the same IRB and regulatory authority review requirements as the original protocol. The Investigator will promptly notify the IRB and DSMB of any SAEs or of any other information that might affect the safe use of the IP during the study. IRB approvals and regulatory authorities' approvals must be sent to the DSMB, or its designee, before initiation of the study or before an amendment is instituted. All correspondence with the IRB and the regulatory authority must be retained in the study regulatory files.

15.1.3 Informed Consent/Assent and Authorization for Use and Disclosure of Protected Health Information

Written informed consent from each subject's parent(s) or legal guardian(s) and written assent from each subject, if applicable, must be obtained before any study-specific screening or Baseline period evaluations are performed. One copy of the signed informed consent/assent documents will be given to the subject; the Investigator will retain the original copies of these documents.

The informed consent/assent documents, as prepared by the Study Sponsor or designee, must be reviewed and approved by the IRB and regulatory authorities, as applicable, before initiation of the study. The informed consent document must contain the basic required elements of consent and additional elements, as applicable, as specified in the 21 CFR 50.25.

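### Section 11.5 allows 5 business days to tell the DSMB of a related fatal or life-threatening SAE; 24 hours would suit weekly dosing better

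*Combined protocol and SAP*

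**What the plan says.** Section 11.5 sets two limits for reporting SAEs to the DSMB. For an event that is fatal or life-threatening and at least possibly related to a study drug, the report is due as follows: "regardless of expectedness, will be reported to the DSMB within 5 business days of initial receipt of the information". For a SUSAR, "but is not fatal or life-threatening, will be reported within 5 business days of initial receipt of the information".

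Section 11.5.2 covers pregnancy, overdose, medication error and accidental or occupational exposure. These events, "regardless of whether an AE or SAE has occurred) must be reported to the DSMB within 24 hours of notification". Section 11.5.2.2 repeats this for overdose: "An overdose will be recorded on the appropriate form and sent to the DSMB or designee within 24 hours".

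On dosing, Section 8.2 states: "Subjects should receive study treatment once every 7 days starting at the Week 1 Visit". Section 13.3.1 says that the DSMB "will act in an advisory capacity to review participant safety and study progress", and leaves detail to another document: "The activities and composition of this committee will be detailed in the DSMB Charter". Section 15.1.2 adds a general duty with no time attached: "The Investigator will promptly notify the IRB and DSMB of any SAEs".

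**The concern.** The gravest related events have no faster route to the DSMB than a SUSAR that threatens nobody's life, and a slower one than an overdose that did no harm. The FDA limits in the same section are graded by gravity; the DSMB limits are not.

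The length matters because the limit is about as long as the dosing interval. Roughly six boys receive three drugs of one class. After a related death or life-threatening reaction in one boy, the question for an independent safety adviser is whether the others should have their next infusion. Under the stated limit the DSMB may first hear of the event after those infusions have been given, too late to advise on them.

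**Working it through.** **1. The limits side by side**

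| Event | Recipient | Limit | Section |
|---|---|---|---|
| Related fatal or life-threatening SAE, expected or not | DSMB | 5 business days | 11.5 |
| SUSAR, not fatal or life-threatening | DSMB | 5 business days | 11.5 |
| Overdose, with or without an AE | DSMB | 24 hours | 11.5.2, 11.5.2.2 |
| Fatal or life-threatening SUSAR | FDA | 7 calendar days | 11.5 |
| SUSAR, not fatal or life-threatening | FDA | 15 calendar days | 11.5 |
| Any SUSAR | Manufacturer | 24 hours | 11.5 |

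The difference by gravity is 15 − 7 = 8 calendar days for the FDA and 5 − 5 = 0 business days for the DSMB.

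**2. Five business days in calendar days**

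Counting starts on the day after receipt.

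| Day of receipt | No holiday | One weekday holiday in the count |
|---|---|---|
| Monday to Thursday | 7 | 8 |
| Friday | 7 | 10 |
| Saturday | 6 | 9 |
| Sunday | 5 | 8 |

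For Friday, the holiday pushes the fifth business day past a second weekend: 7 + 3 = 10. The same weekend explains Saturday (6 + 3 = 9) and Sunday (5 + 3 = 8). Without a holiday, the limit is 5 to 7 times the 24 hours allowed for an overdose.

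**3. Infusions that fall inside the limit**

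Take weekday receipt with no holiday, so the deadline is day 7. On the nominal schedule of one infusion per 7 days, days 1 to 7 contain exactly one infusion for each boy, whichever weekday he is dosed.

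Other boys exposed = n − 1, where n is the number on treatment at once. Enrolment timing is not given, so n is an assumption: n = 2 gives 1 and n = 6 gives 5.

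This count includes an infusion due on the deadline day itself. It also includes one due on day 1, which could precede a 24-hour notice as well. The part of the week in which the two limits differ is therefore days 2 to 7, or 6 of the 7 possible dosing days (5 of 7 if the deadline day is left out). The ±2-day window in Section 8.2 can move a given infusion into or out of the period.

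**4. Whether another section sets a shorter time for this notice**

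- Section 15.1.2 asks for prompt notice but gives no number.
- Section 11.5.2.3 (Death) stands under Special Situations, but death is not in the list to which the 24 hours apply, and the subsection sets no time.
- Section 7.5 lets the Sponsor/Investigator stop any subject, without a DSMB notice time.
- Section 7.6 calls for DSMB consultation before the study is halted, also without a time.
- Section 8.2.1 requires DSMB consultation only when an AE has interrupted 2 or more consecutive doses in the same subject.
- Section 11.5 stops the product for a related SAE during administration; this does not concern notice.
- Section 13.4 provides status reports every 6 months or on request.
- Section 15.1.4 covers emergency departures for one subject and asks for DSMB contact without a number of hours or days.

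None sets a time limit, so Section 11.5 governs.

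**The case against.** Five business days is a maximum, it equals the IRB limit in the same section, and the revision record says Section 11 was aligned with local IRB guidance, so it was probably chosen deliberately. Read with Section 15.1.2, the duty is prompt notice with an outer limit. The study has one centre, and the clock starts when the Investigator's own team learns of the event; the Investigator can stop dosing at once. That stands, and it is why this is an improvement rather than an error.

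An overdose is a fact entered on a form, whereas a related SAE needs a causality judgement and a report with 14 listed items (Section 11.5.1). Different content can justify different limits. That is fair, but Section 11.5.1 already separates initial from follow-up reports, and an unexpected related death must reach the manufacturer within 24 hours anyway.

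The DSMB responsibilities section mentions a non-voting manufacturer member, who might pass such news on. That member's stated duty concerns other trials, and an expected related death goes to the manufacturer only on the monthly listing. This does not guarantee notice to the board.

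Shortening one bullet leaves a non-fatal SUSAR slower than a harmless overdose. That is true. The case for the change rests on the events most likely to call for advice before the next dose, not on making every limit consistent.

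Finally, no infusion is shown to be prevented. That also stands, because notice gives the DSMB only the chance to advise.

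**Conclusion.** The point holds as a modest design improvement. The stated limit lets 7 calendar days pass after weekday receipt, and up to 10 with one holiday, before the DSMB must hear of a related death or life-threatening event. In that time one scheduled infusion can fall due in each of 1 to 5 other boys. This upper bound assumes the nominal 7-day schedule, weekday receipt without a holiday, 2 to 6 boys on treatment at once, notice on the last permitted day and no action by the Investigator. The decision on dosing stays with the Sponsor/Investigator whenever the DSMB is told. The main uncertainty is the DSMB Charter, which was not supplied and may set a shorter limit.

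**What to change.** In the first DSMB bullet of Section 11.5 (related and fatal or life-threatening, whether expected or not), replace 5 business days with 24 hours from initial receipt, with follow-up reports as Section 11.5 already provides. Leave the second DSMB bullet and the IRB, FDA and manufacturer limits as they are. If the DSMB Charter already sets 24 hours or less, align Section 11.5 with it.

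The cost is one deadline in one bullet. The site already has a 24-hour route to the DSMB for special situations. The drawback is that a first report sent within 24 hours will often lack some of the 14 items in Section 11.5.1 and will depend on follow-up to complete them.

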11.5.1 Serious Adverse Event Reporting: Content and Format

The serious adverse event report will include, but need not be limited to: (1) the date of the event; (2) designation of the report as an initial report or a follow-up report, identification of all safety reports previously filed for the clinical protocol concerning a similar adverse event, and an analysis of the significance of the adverse event in light of previous similar reports; (3) clinical site; (4) the Principal Investigator; (5) FDA's Investigational New Drug (IND) application number; (6) Drug name; (7) route of administration, e.g., intramuscular; (8) dosing schedule; (9) a complete description of the event; (10) relevant clinical observations; (11) relevant clinical history; (12) relevant tests that were or are planned to be conducted; (13) date of any treatment of the event; and (14) the suspected cause of the event.

This report will be sent to the IRB, FDA, DSMB and Sarepta according to regulatory requirements described in section Safety Reporting.

11.5.2 Special Situations

All occurrences of pregnancy, overdose, medication error, and accidental or occupational exposure with study treatment (regardless of whether an AE or SAE has occurred) must be reported to the DSMB within 24 hours of notification and to Sarepta on monthly line listings.

